8.7.1 Treatment accountability and compliance

Measures taken to ensure and document treatment compliance and IMP accountability include:

- Proper recording of treatment kit number or packaging number as required on appropriate electronic case report form (e-CRF) page for accounting purposes
- All medication treatment kits (whether empty or unused) are returned by the patient at each visit when a treatment dispensing is planned
- The completed home injection diary (returned to the site at each visit), returned treatment kit boxes and any unused and used vials will be used for drug accountability purposes
- The study coordinator tracks treatment accountability/compliance by diary and by counting the number of used treatment kits and fills in the appropriate page of the patient treatment log
- The monitor in charge of the study then checks the data entered on the IMP administration page by comparing them with the IMP that has been retrieved and the patient treatment log form.

8.7.2 Return and/or destruction of treatments

All partially used or unused treatment kits will be retrieved by the Sponsor or destroyed at study site. A detailed treatment log of the returned IMP will be established with the Investigator (or the pharmacist) and countersigned by the Investigator and the monitoring team. The Investigator will not destroy the unused IMP, used or partially used kits unless the Sponsor provides written authorization.

8.8 CONCOMITANT MEDICATION

A concomitant medication is any treatment received by the patient concomitantly to any IMP(s). All medication taken during the study should be recorded on the corresponding pages of the patient e-CRF.

8.8.1 Prohibited medications

The use of any biologic DMARDs, including but not limited to etanercept, adalimumab, infliximab, anakinra, canakinumab, riloncept, abatacept, rituximab, tocilizumab, and any biologic DMARDs that may become approved during the study is not authorized throughout the study treatment and until 6 weeks following the EOT visit. If any of these treatments are used, the patient should be discontinued from the study treatment and will be asked to perform the scheduled visits and assessments up to EOS visit. (See exclusion criterion E 09 in Section 7.2 for biologic DMARDs off-treatment period).

Treatment with new non-biologic DMARDs should not be initiated during the study. Existing non-biologic DMARDs, such as MTX should be kept at a stable dose unless the patient develops an AE.

Administration of any live (attenuated) vaccine ([Appendix J](#)) is contraindicated until 4 weeks following the last dose of IMP administration

Treatment with anti-IL-6 or IL-6R antagonist therapies, including but not limited to tocilizumab or sarilumab ([E 08](#)).

Treatment with a JAK inhibitor (such as tofacitinib) ([E 10](#)).

8.8.2 Corticosteroids

8.8.2.1 Systemic parenteral and intra-articular corticosteroids

Patients should not receive systemic parenteral glucocorticoids and/or intra-articular glucocorticoid injections (within 4 weeks prior to Baseline), and should not be initiated on new corticosteroids (either systemic or intra-articular) for JIA-related complaints during the 12-week core treatment phase of the study. In the extension period, intra-articular glucocorticoid injections are permitted as clinically indicated for JIA disease flares, if Investigator considers potential benefit outweighs risk of such injection.

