7.2.1 Exclusion criteria related to study methodology

- E 01. Body weight < 10 kg or > 60 kg for patients enrolled in the 3 ascending dose regimen cohorts, then body weight < 10 kg for patients subsequently enrolled at the selected dose regimen cohorts
- E 02. Wheelchair-bound or bed-ridden
- E 03. Diagnosis of JIA subtypes except polyarticular RF-positive (RF+) or RF-negative (RF-) JIA or extended oJIA
- E 04. If non-steroidal anti-inflammatory drugs (NSAIDs) (including cyclo-oxygenase-2 inhibitors [COX-2]) taken, dose stable for less than 2 weeks prior to the Baseline visit and/or dosing prescribed outside of approved label
- E 05. If nonbiologic DMARD taken, dose stable for less than 6 weeks prior to the Baseline visit or at a dose exceeding the recommended dose as per local labeling

- E 06. If oral glucocorticoid taken, dose stable for <2 weeks or dose exceeding equivalent prednisone dose 0.5 mg/kg/day (or 30 mg/day) within 2 weeks prior to Baseline
- E 07. Use of parenteral or intra-articular glucocorticoid injection within 4 weeks prior to Baseline
- E 08. Prior treatment with anti-IL-6 or IL-6R antagonist therapies, including but not limited to tocilizumab or sarilumab
- E 09. Treatment with any biologic treatment for pcJIA within 5 half-lives prior to the first dose of sarilumab as follows (the required off-treatment periods and procedures may vary according to local requirements):
- Etanercept: within 4 weeks
 - Infliximab: within 8 weeks
 - Adalimumab: within 15 weeks
 - Anakinra: within 2 days
 - Canakinumab: within 19 weeks
 - Abatacept: within 10 weeks
 - Rituximab or other cell-depleting agent: within 16 weeks or until total lymphocyte count and CD 19+ lymphocyte count are normalized, whichever is longer
 - Intravenous Ig: within 15 weeks
- E 10. Treatment with a Janus kinase (JAK) inhibitor within 4 weeks prior to the first dose of sarilumab; and treatment with growth hormone within 4 weeks prior to the first dose of sarilumab (the required off-treatment periods and procedures may vary according to local requirements)
- E 11. Treatment with any investigational biologic or non-biologic product ([Appendix J](#)) within 8 weeks or 5 half-lives prior to Baseline, whichever is longer
- E 12. Lipid lowering drug stable for less than 6 weeks prior to Screening
- E 13. Exclusion related to tuberculosis:
- Active TB or a history of incompletely treated TB

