10.3.3 List of criteria for permanent treatment discontinuation

The patient or the parent(s) or the legal guardian(s) may withdraw the patient from treatment with the IMP if they decide to do so at any time and irrespective of the reason. Based on the Investigator's judgment, the patient could be discontinued from the study treatment once his/her condition requires the treatment with prohibited medications (starting new DMARDs, significant increase in glucocorticoids or considering other biologic therapy, etc). All efforts should be made to document the reasons for treatment discontinuation and this should be documented in the e-CRF.

Investigational medicinal product will be permanently discontinued in case of the following events (refer to [Section 10.6](#) for details):

- Clinical significant infections such as opportunistic infections (see [Appendix I](#)) or active tuberculosis
 - The diagnosis of tuberculosis can be made either on symptoms or on a chest radiograph suggestive of active tuberculosis. Patients should be referred to appropriate medical specialists and whenever possible, skin PPD test or blood QuantiFERON-TB test should be performed and the results should be recorded in the e-CRF
 - Culture positive for non-TB mycobacteria
 - The patient is at risk through close contact with a person with active tuberculosis and the patient refuses to undergo tuberculosis evaluation
- Symptoms of systemic hypersensitivity or anaphylactic reactions
- Significant laboratory abnormalities
 - ALT >5 x ULN or ALT >3 x ULN with concomitant total bilirubin >2 x ULN (unless patient with documented Gilbert's Syndrome)
 - neutrophil count <1000/mm³ (Grade 3 or 4 neutropenia) with evidence of infection
 - platelet count <50 000/mm³, or platelet count <100 000/mm³ with evidence of bleeding
- Acute renal failure (refer to [Appendix G](#))
- Pregnancy in female participant

- Use of any biologic DMARDs other than IMP
- Any AEs, per Investigator's judgment that may jeopardize the patient's safety.

Any abnormal laboratory value that is close to the values described in [Appendix G](#) should be immediately rechecked for confirmation. No dose will be given until the results of the confirmation laboratory tests are received. No decision by the Investigator or Sponsor should be made to permanently discontinue the IMP for the concerned patient until the results of the confirmation laboratory test are received.

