**2.4.6.2 Analyses of other efficacy endpoints**

JIA ACR30 core set variable scores and changes from baseline for each dose regimen cohort and weight group will be summarized by visit using means, standard errors, and corresponding 95% CIs. JIA ACR30 response using ESR instead of hs-CRP will be summarized using the same methods as described in the previous section.

JIA ACR50/70/90/100 responses will be summarized using the same methods as described above for JIA-ACR30.

Overall score and change from baseline in JADAS-27 will be summarized by visit (including number, mean, standard error, SD, median, minimum, and maximum) for each dose regimen cohort and weight group (if possible).

Proportions of patients with the low disease activity ( $JADAS-27 \leq 3.8$ ) and inactive disease activity ( $JADAS-27 \leq 1.0$ ) as defined based on JADAS-27 will be explored and summarized. The Kaplan-Meier plot for time to first onset of achieving low disease activity or achieving inactive disease will also be provided.

For the analyses of continuous endpoints including JIA ACR core set variables and JADAS-27, no data will be imputed and the analyses will be done based on data as observed while the patient remains on treatment.

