### 2.5.2 Data handling conventions for secondary efficacy variables

#### *JIA-ACR component – joint counts with active arthritis/limited range of motion (AJC/LJC)*

When calculating the AJC and LJC, the joints with missing assessment will be imputed as the mean of the joints with assessment, ie, the AJC/LJC after imputation are as follows:

$$\text{AJC} = \text{sum (joints with active arthritis='Y')} * (71/\text{number of joints with assessment})$$

$$\text{LJC} = \text{sum (joints with limited motion='Y')} * (67/\text{number of joints with assessment})$$

Please note: the imputation will only be performed if the number of joints with missing assessment is  $\leq 7$  for each active arthritis or limited motion joints. If the number of joints with missing assessment is  $> 7$ , then the corresponding joint counts will be set to missing.

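### In the extension, a joint quietened by a recent intra-articular steroid injection can be credited to sarilumab, because the visible SAP has no rule for injected joints

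*Protocol*

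**What the plan says.** **Rescue.** Under Protocol 8.8.2.1 patients "should not be initiated on new corticosteroids (either systemic or intra-articular) for JIA-related complaints during the 12-week core treatment phase". For the extension the same section says: "In the extension period, intra-articular glucocorticoid injections are permitted as clinically indicated for JIA disease flares", subject to the condition "if Investigator considers potential benefit outweighs risk of such injection". Exclusion E 07 (Protocol 7.2.1) removes candidates with "Use of parenteral or intra-articular glucocorticoid injection within 4 weeks prior to Baseline". Protocol 10.3.3 lets the investigator stop IMP when prohibited treatment is needed. Its examples are "starting new DMARDs, significant increase in glucocorticoids or considering other biologic therapy, etc", and intra-articular injection is not named.

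**Scoring.** SAP 2.5.2 states: "When calculating the AJC and LJC, the joints with missing assessment will be imputed as the mean of the joints with assessment". The JADAS-27 joint count (AJC27) has a matching rule. Neither mentions injected joints.

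**Analysis.** SAP 2.4.6.1 bases the main ACR30 summary on observed on-treatment values. Non-responder imputation, LOCF and the post-discontinuation analysis are confined to the core phase and respond to discontinuation or missing data, not to rescue. For the continuous endpoints, SAP 2.4.6.2 says "no data will be imputed and the analyses will be done based on data as observed while the patient remains on treatment". The same section adds the proportions with JADAS-27 at or below 3.8 and 1.0, and a Kaplan-Meier plot to the first such visit.

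**The concern.** A child who starts another biologic must stop IMP (Protocol 8.8.1), so later visits leave the on-treatment summaries. A child whose flaring joint is injected stays on IMP, and the next joint count enters as observed. The protocol guards efficacy assessments against a weaker influence: Protocol 8.8.4 asks that analgesics be avoided in the 6 hours beforehand. It sets no corresponding separation between an injection and the extension joint counts.

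At stake is how the long-term efficacy summaries can be read. There is no comparator arm in which the same rescue effect would appear, so a reader could not separate response on sarilumab from response on sarilumab plus local steroid.

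**Working it through.** The plan states no figure for this point, so there is none to reproduce. The steps below check the scoring and then bound the exposure.

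**1. Denominators.** The joints listed in Protocol 9.4.1.4 sum to 71. Removing the four sternoclavicular and acromioclavicular joints leaves 67. The JADAS-27 joints sum to 1+2+2+6+10+2+2+2 = 27. The SAP denominators are correct.

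**2. One injected joint and the active joint count (AJC).** Improvement = (baseline − current)/baseline. Suppose one of the currently active joints is injected and goes quiet (illustrative counts; 5 is the entry minimum):

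| Baseline, active before injection | SAP as written | Injected joint set to missing and prorated | Injected joint kept as active |
|---|---|---|---|
| 10, 8 | (10−7)/10 = 30.0% | 7×71/70 = 7.10, so 29.0% | (10−8)/10 = 20.0% |
| 5, 4 | (5−3)/5 = 40.0% | 3×71/70 = 3.04, so 39.1% | (5−4)/5 = 20.0% |

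One joint can carry this component to the 30% threshold. Applying the existing missing-joint rule to it would correct almost nothing.

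**3. ACR response.** Three of six components must improve, and joint counts supply at most two. The limited-motion count (LJC) need not fall, because motion can stay limited in a quiet joint. At least one of the two globals, CHAQ-DI or hs-CRP must also improve.

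**4. JADAS-27.** Each active joint adds one point to a sum with maximum 10+10+27+10 = 57. In a constructed case with two active knees, both globals 1.0 and inflammation item 0, the score is 2+1+1+0 = 4.0, above 3.8. With both knees quiet after injection it is 0+1+1+0 = 2.0, which counts as low disease activity and, if it is the first such visit, as a permanent Kaplan-Meier event.

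**5. Exposure.** Assumptions, none from the documents: 90 extension patients, 5-20% injected, one randomly timed injection each, 4-week window.
- Dose-finding and second portions (efficacy visits at Weeks 24, 48, 72, 96, 120, 144, 156): 7×4 = 28 of 144 weeks = 19.4%.
- Third portion (Weeks 24, 48, 72, 96): 4×4 = 16 of 84 weeks = 19.0%.
- Injected children: 0.05×90 = 4.5 to 0.20×90 = 18.
- Injected within a window: 4.5×0.194 = 0.9 to 18×0.194 = 3.5, or about 1 to 4 children over the whole extension. That is at most 0.9/90 = 1% to 3.5/90 = 4% of patients.
- At any single visit: at most 18×4/84 = 0.9 of a child on average.

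On these schedules the count grows in proportion to the window, up to the 12-week gap between Weeks 144 and 156. Repeat injections, and the denser early visits of children switched to the selected dose, would raise it.

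**The case against.** The case on the other side is substantial. Efficacy is secondary, descriptive and untested, and the SAP names safety and local tolerability as the extension's primary objectives. Summarising observed values with permitted rescue is a legitimate descriptive choice. Concomitant medication is recorded with start dates, and corticosteroid use is tabulated. A flare bad enough to inject may also worsen other joints, the globals or hs-CRP, and the ACR rule penalises worsening. In the first two portions only Week 12 ACR30 responders enter the extension. The Kaplan-Meier plot counts first onset, so a child who reached low activity before flaring is already an event. The JADAS example sits close to the cut-off by construction.

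All of this limits the size. It does not supply a rule: in the visible text the corticosteroid table is not linked to joints or visits.

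Three stronger readings are tempting, and the documents do not support them:
- **That injections are unlimited.** A JIA flare and a favourable benefit-risk judgment are both required. What is absent is a cap on number, joints or timing.
- **That long-term response is inflated as a matter of fact.** With no injection rate given, only a possible upward bias follows.
- **That an injection can by itself make an ACR responder.** Step 3 rules that out if it acts on joint counts alone.

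It is also fair to object that carrying forward the last recorded joint status would often fail. Most extension joint counts are 24 weeks apart, so that status may predate the flare and read inactive. The fix avoids this. Oral steroid increases for flare (Protocol 8.8.2.2) are a separate rescue effect that it does not address.

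**Conclusion.** The gap is real and modest. As written, the plan can credit a local steroid effect to sarilumab in extension AJC, AJC27 and JADAS-27, in the proportions at or below 3.8 and 1.0, in the first-onset Kaplan-Meier plot and, through one component, in ACR response. The likely direction is upward and the amount is unknown. Under the stated assumptions about 1 to 4 children are exposed over the extension, and fewer than one on average at any single visit. The Kaplan-Meier plot is the most sensitive output, because one transient visit becomes a permanent event.

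The primary PK endpoint and Week 12 efficacy are outside the problem if the core-phase ban is followed, and no error rate or power is involved. Parts of the SAP are redacted, so the conclusion is limited to its visible text. The protocol gives no reason for E 07, so using its 4 weeks as the period of joint distortion is a working choice.

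**What to change.** Add to SAP 2.5.2 and 2.4.6 a pre-specified supplementary analysis for extension visits within 4 weeks after an intra-articular glucocorticoid injection (the E 07 interval), with a longer window as sensitivity. In it:

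- Score the injected joint as active in AJC and AJC27.
- If the injected joint was not recorded, count the visit as non-response for ACR, as not reaching either JADAS-27 cut-off, and as no Kaplan-Meier event.
- Do not carry forward the last recorded joint status, and do not prorate the joint as missing.

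Report the results beside the as-observed ones, and record the injected joint with the medication date. Scoring the joint as active is deliberately conservative: it assumes the joint would have stayed active without the injection.

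The cost is one SAP rule, one CRF item and a slightly lower extension response in the supplementary analysis. The use of injections remains the investigator's decision, and nothing in the clinical conduct changes.

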8.8.2.2 Oral corticosteroids

Oral steroids may be increased at any time for flare. Oral corticosteroids are permitted if not exceeding 0.5 mg/kg/day (or 30 mg/day) oral prednisone or equivalent at stable dose for at least 2 weeks prior to the Baseline visit.

No change is permitted during the 12-week core treatment phase unless the patient develops an AE (excluding worsening JIA). The dose may be tapered during the extension phase as per the Investigator's recommendations.

If the patient develops an AE for a condition not related to pcJIA that requires a corticosteroid dose modification (eg, increase, or decrease of current concomitant oral prednisone or equivalent), or the introduction of a new oral steroid medication, the dosage modification and AE must be recorded on the patient e-CRF. Furthermore, if this AE occurs during the 12-week core treatment phase, the Sponsor must be notified at the time of the steroid dose modification (eg, within one working day) to verify that the patient can continue to participate in the study.

Glucocorticoid tapering is allowed during the extension phase as per the Investigator's judgment.

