8.8.3 Nonsteroidal anti-inflammatory drugs

Non-steroidal anti-inflammatory drugs (NSAID) and COX-2 are permitted if taken at a stable dose for at least 2 weeks prior to Baseline. The dose used should be in accordance with the approved dose in the country in which the study is conducted. No change is permitted during the 12-week core treatment phase, unless the patient develops an AE (generally requiring a lowering or discontinuation of NSAID/COX-2 treatment). Patients should not be initiated on new NSAIDs/COX-2 during their participation in the 12-week core treatment phase.

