11.4.2.1 Analysis of primary efficacy endpoint(s)

Analysis of JIA ACR30 response is provided in this study section.

Patients achieving JIA ACR30 response for each dose regimen cohort, overall, and by weight group will be summarized by visit using counts, proportions and 95% CIs. All observed data, while the patient remains on treatment will be included in this analysis. No missing data will be imputed. Additionally, for the summaries on the JIA ACR 30 responses during the 12-week core treatment phase, several different approaches will be used for the handling of treatment discontinuations and missing data.

Non responder imputation:

In general, number of joints with active arthritis, number of joints with limited range of motion, and at least 3 of the remaining 4 ACR components at Baseline and a time point are required to determine responder status.

In this method of missing data handling, the data collected after treatment discontinuation will be set to missing. No imputation of missing post baseline values will be performed. Responder status will be determined using available data and patients will automatically become non responders for all time points beyond the time point they discontinued study treatment or for which there is insufficient data.

LOCF approach:

In this method of missing data handling, the missing data will be imputed using the LOCF procedure from the point of treatment discontinuation for all 6 ACR components for all visits post that point. Responder status will be determined using the imputed data.

In this approach, patients with insufficient data after imputation (ie, number of joints with active arthritis, number of joints with limited range of motion, and at least 3 of the remaining 4 ACR components) at baseline and a time point will be considered as non responders at that time point.

As observed including post discontinuation follow-up:

All observed data up to Week 12, including those collected after treatment discontinuation, will be included in this analysis. No missing data will be imputed.

Subgroup analyses:

No additional subgroup summaries are planned for the efficacy.

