### 2.4.6.1 Analysis of JIA ACR30 response

Patients achieving JIA ACR30 [REDACTED] response for each dose regimen cohort, overall and by weight group, will be summarized by visit using counts, proportions and 95% CIs. The primary approach will be based on all observed data while the patient remains on treatment. No missing data will be imputed.

Additionally, for the summaries on the JIA ACR30 responses during the 12-week core treatment part, several different approaches will be used for the handling of treatment discontinuations and missing data.

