#### *Non-responder imputation approach:*

In general, number of joints with active arthritis, number of joints with limited range of motion, and at least 3 of the remaining 4 ACR components at baseline and a time point are required to determine responder status.

In this method of missing data handling, the data collected after treatment discontinuation will be set to missing. No imputation of missing post-baseline values will be performed. Responder status will be determined using available data and patients will automatically become non-responders for all time points beyond the time point they discontinued study treatment or for which there is insufficient data.

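### Protocol 8.8.2.2 gives opposite rules for raising oral steroids when JIA flares in the 12-week core; separately, the supplementary non-responder analysis could be improved to count corticosteroid rescue as non-response

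*Protocol*

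**What the plan says.** **Steroid rules.** Protocol 8.8.2.2 first states "Oral steroids may be increased at any time for flare", with no limit to a study phase. Its second paragraph states "No change is permitted during the 12-week core treatment phase unless the patient develops an AE (excluding worsening JIA". Three other sections bear on the same event:

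- Protocol 8.8.2.1: patients "should not be initiated on new corticosteroids (either systemic or intra-articular) for JIA-related complaints during the 12-week core treatment phase of the study". The same section allows intra-articular injections for flare in the extension.
- Protocol 8.8.3, on NSAIDs: "No change is permitted during the 12-week core treatment phase, unless the patient develops an AE".
- Protocol 10.3.3: on the investigator's judgment, a patient "could be discontinued from the study treatment once his/her condition requires the treatment with prohibited medications (starting new DMARDs, significant increase in glucocorticoids". No threshold for a significant increase is given.

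**ACR response.** SAP 2.4.6.1 names the main analysis: "The primary approach will be based on all observed data while the patient remains on treatment". For the core it adds three further approaches: non-responder imputation (NRI), last observation carried forward, and all observed data including those after discontinuation. The NRI rule in protocol 11.4.2.1 is "patients will automatically become non responders for all time points beyond the time point they discontinued study treatment or for which there is insufficient data". The SAP repeats it: "patients will automatically become non-responders for all time points beyond the time point they discontinued study treatment", or where data are insufficient.

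**Reporting.** SAP 2.2 tabulates critical or major deviations. SAP 2.4.2 tabulates concomitant corticosteroids. Protocol 8.8 requires all medication to be recorded in the e-CRF.

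**The concern.** A child flares at Week 6. One sentence of 8.8.2.2 lets the site raise the oral steroid; the next paragraph forbids it. Different sites may act differently, and a site that follows the first sentence would have no reason to report a deviation.

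The second issue is how such a child is counted. The study is open-label and has no placebo arm, and its response rates are read in small cells by regimen and weight group. If the child stays on sarilumab and later meets the ACR criteria, part of the response may be due to the added steroid, and the visible tables would not show it.

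**Working it through.** **Step 1: the rules side by side, for an oral steroid increase because of a JIA flare in the core**

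| Source | What follows |
|---|---|
| Protocol 8.8.2.2, first sentence | Allowed |
| Protocol 8.8.2.2, second paragraph | Not allowed; worsening JIA is excluded as a reason |
| Protocol 8.8.2.1 | Starting a new steroid for JIA is barred |
| Protocol 8.8.3 | Parallel no-change rule for NSAIDs |
| Protocol 10.3.3 | A significant increase is grouped with prohibited medication; stopping drug is optional |

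The first two rows cannot both hold. The last three agree with the second, which is also the more specific, so the ban looks intended. No visible text says which sentence prevails.

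**Step 2: the same child in each ACR approach, if she stays on drug with enough component data**

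| Approach | What changes her status | Does a steroid increase count? |
|---|---|---|
| Observed, on treatment (primary) | Leaving treatment | No |
| NRI | Stopping drug, or insufficient data | No |
| Last observation carried forward | Stopping drug, or insufficient data after imputation | No |
| Observed, including after discontinuation | Missing data only | No |

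She is judged on her observed components in all four and can be a responder in each.

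**Step 3: who a wording change can still reach.** Protocol 4.3.2 starts the third portion once enrollment of the first two is complete, and the third-portion flow chart (1.2.2.3, footnote g) already fixes dosing every other week. A new sentence therefore mainly governs third-portion patients in their core phase.

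**Step 4: scale.** The plan states no figure for steroid increases, so there is none to reproduce. Its cohort counts do agree: 3 regimens × 2 groups × 6 = 36; 36 + 24 = 60 evaluable; 6 + 12 = 18 per weight group at the selected regimen; 72 + 28 = 100 treated.

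Reclassifying one child moves a rate by 100/n points:

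| Cell | n | Points per child |
|---|---|---|
| One regimen and weight group, evaluable | 6 | 16.7 |
| Selected regimen, one weight group, evaluable | 18 | 5.6 |
| The first cell, treated | 6 × 72/60 = 7.2 | 13.9 |
| The second cell, treated | 18 × 72/60 = 21.6 | 4.6 |
| Selected regimen with third portion, treated | 21.6 + 8 = 29.6 to 21.6 + 20 = 41.6 | 3.4 to 2.4 |
| The same, if an intermediate regimen is selected | 14.4 + 8 = 22.4 to 14.4 + 20 = 34.4 | 4.5 to 2.9 |

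The treated rows are shown because the efficacy population is everyone dosed (SAP 2.3.3). They assume that the 72 enrolled are all treated and spread evenly. The 8 and 20 come from the third-portion cap in protocol 8.4. The 14.4 is the second portion alone, 12 × 1.2.

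As an invented example, 15 of 18 responders is 83.3% (exact 95% CI 58.6 to 96.4). With one child reclassified, 14 of 18 is 77.8% (52.4 to 93.6). The change is visible but well inside the interval.

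**The case against.** **The ban is clear in context.** Even a steroid change for an adverse event unrelated to JIA must be notified to the sponsor during the core (8.8.2.2), and the neighbouring sections point the same way. This stands as evidence of intent. It does not remove an explicit contrary permission in the same section, and the notification rule does not cover a flare.

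**NRI is not wrong.** A reader might infer that leaving steroid rescue out of NRI is a mistake. The documents do not support that. Both introduce the extra approaches as ways to deal with patients who stop drug or lack data, and NRI does this. Counting rescue as non-response is one legitimate choice; judging on the observed outcome is another.

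**Once the sentence is corrected, an increase for flare is a deviation**, like a new NSAID or DMARD. This is fair, but the deviation table covers only critical or major deviations and is not tied to ACR status. For the same reason, an NRI rule cannot be justified as covering only what 8.8.2.2 permits, because 8.8.2.1 already bars new starts and intra-articular injections in the core. The sound reason is that corticosteroid rescue for JIA can itself improve the ACR components.

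**The public copy is incomplete.** SAP 1.5, 1.6, 2.4.7 and 2.4.11 and protocol Appendices K and L are listed in the contents, but their text is not available. A relevant rule there cannot be excluded, so the negatives here apply to the visible text only.

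**Conclusion.** Protocol 8.8.2.2 is wrong as written and should be clarified. The steroid rule for NRI and the listing are an inexpensive improvement.

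A reader might infer more: that reported ACR rates are inflated, or that the trial's main result is at risk. Neither is supported. The documents give no rate of steroid increase, so the shifts per child show scale and do not estimate bias. The primary endpoint is PK, efficacy is secondary and descriptive, and no hypothesis is tested. The proposed NRI rule changes neither the as-observed primary ACR result nor entry to the extension. The Week 12 ACR30 condition for entry applies only to the first two portions.

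For the patients whom a wording change can still reach, one child is worth about 2.4 to 3.4 points, or 2.9 to 4.5 if an intermediate regimen was selected. Both ranges rest on the even-spread assumption. The larger figures of 16.7 and 5.6 belong to cells of 6 and 18 evaluable patients from the first two portions.

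**What to change.** 1. **Protocol 8.8.2.2.** Replace the first sentence with: *In the extension phase, oral steroids may be increased for flare.* This needs ethics approval and can go with the next amendment.
2. **Supplementary NRI only (improvement).** Add to protocol 11.4.2.1 and SAP 2.4.6.1: *A patient is a non-responder at all core visits after a systemic steroid start or increase, or an intra-articular steroid injection, given for JIA.* State the reason as covering corticosteroid rescue for JIA. If only the SAP is changed, it should record the departure from the protocol.
3. **Listing.** Show these patients by regimen and weight group with their ACR status, beside the as-observed primary result, which stays as planned.

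The cost is one protocol sentence, one line in each document and one listing. No new data are needed: all medication is recorded, and SAP 2.1.2 already distinguishes steroids given as treatment for JIA. Items 2 and 3 apply to core data from every portion, whatever enrollment remains. The downside is that the NRI rate may be slightly lower.
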